2.0 OVERALL OBJECTIVES

The study will evaluate the outcome of nasal obstruction treated with the Vivaer™ Stylus, and also attempt to use computational aerodynamics simulation and sensory measurements to identify and predict patients' treatment outcome. The ability to envisage variables that will lead to best outcome may have potential to assist patients and clinicians in planning effective, well-informed, personalized treatment/surgery strategies.

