2.1 Primary outcome variables

The primary symptom outcome variables include self-reported Nasal Obstruction Symptoms Evaluation (NOSE) score and VAS of nasal obstruction.

The primary independent objective variables include several categories: 1) variables that index general disease severity (Computerized Tomography (CT) staging and endoscopic examination score), 2) peak inspiratory flow measurements of nasal physical resistance.

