2.2 Secondary outcome variables

Secondary outcome variables will include age, gender, race, duration of the disease, and medical and smoking histories. The potential confounding effect of the secondary outcome variables will be examined.

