4.9 Data Analysis

Treatment effectiveness

Outcome variables: patient's ratings of nasal obstruction via a VAS and NOSE score as well as the SNOT-22 questionnaire and peak inspiratory flow rate. One-way ANOVA with repeated measures will be used to compare post-treatment vs. baseline measurements and determine the effectiveness of the treatment.

Hypothesis:

Nasal valve region airflow and airflow induced cooling is critical for patients' subjective nasal patency.

Many publications suggest that sensory feedback is as important to perception of nasal obstruction as nasal resistance. For example: Topical or oral application of menthol produces the illusion of decongestion and improved nasal airflow without actually altering nasal resistance¹⁰. Topical application of local anesthetics results in an artificial sensation of nasal obstruction, presumably due to blocking of the trigeminal afferents¹¹.

The Ohio State University (OSU) staff have published a series of studies^{6,12,13} with individualized Computational Fluid Dynamics models and demonstrated that nasal cooling during breathing at the nasal valve region and the nasal trigeminal nerve sensitivity are key to the perception or absence of nasal obstruction. The combination of these variables can predict the subject's ratings (excellent, normal and moderately obstructed) with 89.3% success. It is likely that nasal valve width and shape may have an optimal range in order to achieve both low nasal resistance and high regional mucosal cooling (see Fig. 5). This study will examine a broad list of factors that may contribute to patients' subjective outcomes, not just limited to nasal resistance alone, that include CFD simulation of nasal airflow, mucosa cooling and mucosa sensitivity responding to that cooling.

[figure not shown]

Figure 5. Computational simulation of nasal cooling

- a) high regional cooling, no complaints
- b) low nasal cooling with moderate ratings of nasal obstruction

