Spearmen correlation and multiple regression will be used to screen for independent variables that significantly correlate with dependent variables, as well as potential non-linear relationships between the variables. Other potential confounding factors (e.g., age, duration of the disease, smoking history) will also be examined. The Holm Bonferroni correction will be applied to control for multiple comparisons. Finally, statistical learning methods such as linear discrimination analysis (LDA) and logistic regression will be applied for classification and discrimination of patient symptom categories (e.g., symptom-free, moderate and severe nasal obstruction) based on significant independent variables.

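### The outcome-prediction screen does not define its dependent variable or name baseline NOSE/VAS as a covariate, so a variable that only tracks baseline severity can pass as a predictor

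*Combined protocol and SAP*

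**What the plan says.** Section 2.0 sets an aim beyond the before/after comparison: the study will "attempt to use computational aerodynamics simulation and sensory measurements to identify and predict patients' treatment outcome". The only analysis that serves this aim is in section 4.9: "Spearmen correlation and multiple regression will be used to screen for independent variables that significantly correlate with dependent variables". The regression is not written out. The section does not say whether the dependent variable is the day-90 score, the change from baseline or the score at the same visit.

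Covariates are named in two places. Section 4.9 says "Other potential confounding factors (e.g., age, duration of the disease, smoking history) will also be examined". Section 2.2 says "Secondary outcome variables will include age, gender, race, duration of the disease, and medical and smoking histories", and adds that their possible confounding effect will be examined. Baseline NOSE and VAS are in neither list. Section 2.1 gives the two scores an outcome role only: "The primary symptom outcome variables include self-reported Nasal Obstruction Symptoms Evaluation (NOSE) score and VAS of nasal obstruction". Their baseline values enter one stated analysis, the repeated-measures ANOVA for effectiveness, which is separate from the screen.

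Section 4.9 applies Holm-Bonferroni. It gives no alpha, sidedness or number of tests. It then passes the significant variables on to discriminant analysis and logistic regression.

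**The concern.** The protocol itself ties the candidates to baseline severity. Section 2.1 describes one group of independent variables as "variables that index general disease severity (Computerized Tomography (CT) staging and endoscopic examination score". Section 4.9 cites earlier work that "demonstrated that nasal cooling during breathing at the nasal valve region and the nasal trigeminal nerve sensitivity are key to the perception" of obstruction, with 89.3% success in predicting subjects' ratings. That percentage is a classification rate and gives no correlation for this study. It does suggest that pre-treatment values of such variables will follow the pre-treatment symptom score.

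Suppose a candidate tells us nothing about day 90 once the baseline score is known. It can still correlate with the day-90 score, because patients tend to keep their rank. It can also correlate with change, because high starters tend to fall further. The two correlations have opposite signs, so the same variable could look favourable or unfavourable depending on an outcome definition that the plan leaves open.

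At stake is the prediction claim. Information that the clinician already has from a questionnaire could be credited to CFD, CT or peak flow and carried into the classification step.

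**Working it through.** The plan states no power, alpha, SD or correlation, so there is no figure of its own to reproduce.

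**Inputs from the documents.** n = 20 (the maximum in section 4.2); entry requires NOSE of at least 60 (section 4.3); Holm correction (section 4.9).

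**Assumptions.** Two-sided 0.05 per test; normal scores with equal variance at both visits; r = correlation of candidate X with baseline score Y0; ρ = correlation of Y0 with day-90 score Y1; X independent of Y1 given Y0.

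**Closed form.**
- Level: corr(X, Y1) = rρ.
- Change: the covariance is rρ − r = −r(1−ρ) and the variance of change is 2(1−ρ), so corr(X, Y1−Y0) = −r√((1−ρ)/2).
- Given Y0, the partial correlation is 0 by construction.
- At r = 0.6, ρ = 0.5: level 0.6 × 0.5 = 0.30; change −0.6 × √0.25 = −0.30.

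**Simulated per-test false-positive rate (%)**, n = 20, 40,000 runs per cell. Level and change use unadjusted Spearman; adjusted is the regression of Y1 on X and Y0. The last two columns keep only the upper half of baseline scores, as an assumed stand-in for the NOSE threshold, with r and ρ as pre-selection values.

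| r | ρ | Level | Change | Adjusted | Level, upper half | Change, upper half |
|---|---|---|---|---|---|---|
| 0.3 | 0.3 | 6.5 | 10.8 | 4.9 | 5.4 | 5.9 |
| 0.3 | 0.5 | 9.3 | 9.1 | 5.1 | 5.7 | 5.8 |
| 0.3 | 0.7 | 13.0 | 7.4 | 5.0 | 6.7 | 5.4 |
| 0.5 | 0.3 | 9.2 | 22.1 | 5.2 | 5.9 | 8.2 |
| 0.5 | 0.5 | 16.8 | 16.6 | 5.2 | 7.0 | 7.2 |
| 0.5 | 0.7 | 29.3 | 11.8 | 4.9 | 10.0 | 6.3 |
| 0.7 | 0.3 | 13.2 | 40.3 | 5.1 | 6.5 | 12.7 |
| 0.7 | 0.5 | 29.5 | 29.7 | 5.0 | 9.6 | 10.1 |
| 0.7 | 0.7 | 54.9 | 19.1 | 5.0 | 17.1 | 7.7 |

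At r = 0 all rates are about 5%. Over r = 0.4-0.8 and ρ = 0.3-0.7 the ranges are about 8-69% (level) and 9-52% (change) without range restriction, and about 5-24% and 6-17% with it. At r = 0.6, ρ = 0.5 the rate is about 23% for either outcome, or about 8% with restriction.

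**Effect of Holm.** With an assumed 8 tests, the first step is 0.05/8 = 0.00625. At r = 0.6, ρ = 0.5, one such candidate passes that step about 6.4% of the time, or 1.5% with restriction. If all 8 candidates only track baseline, the unrestricted family-wise rate at r = ρ = 0.5 is about 25% for level or change, against 5.0% with baseline adjustment.

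**The case against.** **The exclusion is not written.** A reader might infer that the plan has decided to keep baseline out of the model. The documents do not support that. The list in section 4.9 is introduced as examples, no model is stated, and nothing bars baseline NOSE or VAS. The section 2.2 list has no such qualifier, but it is headed as outcome variables and is not a model statement. The fault is missing specification. This stands.

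**Another reading is open.** The hypothesis in section 4.9 concerns airflow, cooling and perceived patency, CFD is run on the scan from each visit, and the last step classifies symptom categories. All of this also fits same-visit associations, where following concurrent severity is the hypothesis and no artefact. This stands, but same-visit association alone would not deliver the prediction aim of section 2.0.

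**The size can be overread.** A reader might take 23% as the rate at which the planned procedure would declare one candidate. It is a per-test rate before Holm and without range restriction. The NOSE threshold narrows baseline NOSE. VAS has no entry threshold, although selection on NOSE would narrow VAS too, so far as the two move together.

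**A marginal predictor still predicts.** A variable correlated with the day-90 level does predict that level, and section 2.0 does not ask for value beyond the questionnaire. This is fair. What lacks support is crediting the candidate with information that the baseline score already carries.

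**Adjustment is not perfect.** If the candidate tracks true severity and the score's reliability is 0.7-0.8 (assumed), the adjusted rate at r = 0.6, ρ = 0.5 is still about 11% to 7%.

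**Conclusion.** The point holds for the prediction aim, as a gap in specification. Spearman correlation as planned carries no adjustment, and no covariate list names the baseline score. If pre-treatment candidates are tested against day-90 level or change, the screen can credit a variable that only restates baseline severity. The inflation may be slight or severe: the ranges above rest on assumed correlations, and for NOSE the lower, range-restricted set is the more relevant. Holm corrects for the number of tests and leaves the confounding in place.

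A reader might also infer that the effectiveness result is compromised. The documents do not support that: the before/after ANOVA is a separate analysis that this gap does not touch. Same-visit associations are not affected either.

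The sponsor should correct this before the screen is run. Direction and remedy are clear; the size is uncertain.

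**What to change.** In section 4.9:
- Define the prediction outcome as the day-90 NOSE score, and likewise the day-90 VAS score.
- Fit one regression per pre-treatment candidate, with the matching baseline score forced in. At n = 20 this leaves 20 − 3 = 17 residual degrees of freedom. Test the candidate's coefficient.
- Use partial Spearman correlation given baseline as the rank version.
- Apply Holm across those tests, and state their number and the alpha.
- Keep unadjusted correlations with level or change as descriptive, and state same-visit associations as a separate question.
- Label the screen exploratory and keep the candidates few.

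In section 2.2, add baseline NOSE and VAS to the covariates. Also state which NOSE measurement is the baseline: Table 1 marks NOSE at screening, while the text of section 4.7 lists it among the baseline-visit procedures.

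The cost is a few sentences and one degree of freedom per model, with no new data. Some apparent predictors will disappear, and measurement error in the baseline score will leave some confounding, which the report should acknowledge.

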4.2 Study Size

Up to Twenty (20) patients meeting the inclusion/exclusion criteria will be recruited.

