4.6 Measurement / Instrumentation

Endoscopic Examination

Patients will receive endoscopic examination as part of their standard clinical care. The severity of disease will be scored based on endoscopic examination (Lund-Kennedy endoscopic scores).

Study Procedures

Each visit is expected to last 2-3 hours and may include the following procedures. (These procedures are routinely performed for research purposes; however, none of them should be considered standard clinical care. The differences will be explained to the participants during the consent process.)

1. All participants will be asked to fill out a medical history questionnaire, as well as the Sino-Nasal Outcome Test (SNOT-22) questionnaire, the NOSE score and the Visual Analog Scale for nasal obstruction. The SNOT-22 and NOSE are two commonly used validated outcome questionnaires to evaluate change in rhinosinusitis and/or nasal obstruction symptoms in patients. The VAS is a self-rating of nasal obstruction on a linear scale (range 0-10; 0 being completely clear and 10 being completely blocked) using both nostrils and then with the left and right nostril separately.
2. Peak nasal inspiratory flow: A mask attached to a spirometer is fitted tightly on each subject's face without touching the nose. The subject is instructed to inhale as strongly as possible, and the peak flow rate is then recorded. The test will be repeated three (3) times and the results averaged. For unilateral recording, one nostril is blocked with a tape, so that the subject can only inhale through the other nostril.

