3. Research CT scans: The subject may receive a CT scan for non-clinical purposes with a cone beam office CT scanner (3D Accuitomo 170, J. Morita USA, Inc.) at the Department of Otolaryngology at The Ohio State University School of Medicine. This scan has a radiation dosage of roughly 12% that of a conventional head CT scan with a significantly lower associated health risk, while retaining excellent air-mucus contrast for CFD modeling. The recruitment strategy will reduce the need for research CTs and unnecessary radiation by recruiting patients who have been prescribed a sinus CT clinically, which will serve as the subject's baseline CT. Furthermore, if a post-treatment/surgery CT scan is clinically necessary for a patient after enrollment, it will be scheduled for the subject's second study visit. Through these measures, the need for research CT scans will be reduced to limit the number of research CT scans for all patients to one (1).
4. CFD Modeling: 3D numerical nasal models that are suitable for numerical simulation of nasal airflow and odorant transport will be constructed based on each subject/patient's CT scan and according to the method described by Zhao⁸. In brief, first the interface between the nasal mucosa and the air is delineated (using AMIRA[®]) on the CT scans. Then, the nasal cavity air space is filled with tetrahedral elements (ICEMCFD[®]). A finer mesh (prism layer) is created near the mucosal surface to more accurately model the rapidly changing near-wall air velocity and odorant concentration. Next, inspiratory and expiratory quasi-steady laminar nasal airflow^{8,9} is simulated (Fluent[®], Ansys Inc, USA) by applying a physiologically realistic pressure drop between the nostrils and the nasal pharynx. By varying the pressure drop and computing the changes in total airflow through the nose, the total nasal resistance can be determined, a numerical method of rhinomanometry. Through simulation, the following variables will be obtained: numerical nasal resistance, nasal mucosal cooling rate, and nasal airflow distribution patterns.

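### The one stated hypothesis, on nasal-valve airflow and cooling, has no test of its own and can be tested only inside a Holm-corrected screen whose family is undefined

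*Combined protocol and SAP*

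**What the plan says.** Section 4.9 (Data Analysis) has one statement under its hypothesis label: "Nasal valve region airflow and airflow induced cooling is critical for patients' subjective nasal patency". No cooling or airflow metric, symptom score, visit or test is attached to it. The repeated-measures ANOVA in the same section addresses treatment effectiveness, which is a different question.

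The only matching analysis comes later in 4.9, where Spearman correlation and multiple regression "will be used to screen for independent variables that significantly correlate with dependent variables". Possible confounders are also to be looked at. Then: "The Holm Bonferroni correction will be applied to control for multiple comparisons". The plan does not say which tests form the Holm family, how many there are, or whether any is tested first. Discriminant analysis and logistic regression follow, using whichever variables come out significant.

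Section 4.6 lists the outputs of the airflow simulation as "numerical nasal resistance, nasal mucosal cooling rate, and nasal airflow distribution patterns". The VAS is rated "using both nostrils and then with the left and right nostril separately", and peak flow can be recorded for each nostril. Section 4.2 sets the size: "Up to Twenty (20) patients meeting the inclusion/exclusion criteria will be recruited". There is no power statement.

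**The concern.** A hypothesis stated in advance is normally given its own test. Here, on the natural reading, the cooling-symptom correlation competes on equal terms with every other correlation in the screen. With at most 20 patients, that correction can turn a real, moderate association into a non-significant result.

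Because metric, score, visit and family are all open, the answer to the hypothesis also depends on choices that could be made after the data are seen. Both a positive and a negative result would be hard to interpret.

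**Working it through.** The plan has no figure for this analysis to reproduce, so the check asks what the correction costs over a range of plausible families.

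**Inputs from the documents**
- Patients: at most 20 (4.2).
- Predictors: three simulation outputs (4.6), plus CT staging, endoscopic score and peak inspiratory flow (2.1), making six.
- Symptom scores: NOSE and VAS (2.1), with SNOT-22 as a third (4.9).
- Further variables: age, gender, race, disease duration, medical history and smoking history (2.2), making six.

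**Assumptions**
- Two-sided family alpha of 0.05.
- 20 complete pairs, one value per patient.
- True rho of 0.5 to 0.7.

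**Family size m (assumed)**
- 3 simulation outputs × 2 scores = 6
- 6 predictors × 2 scores = 12
- 6 predictors × 3 scores = 18
- (6 + 6) variables × 3 scores = 36

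**First Holm step and critical |r| at n = 20.** The step is 0.05/m, and critical r = t/√(18 + t²).
- m = 1: 0.05, r = 0.444
- m = 18: 0.0028, r = 0.632
- m = 36: 0.0014, r = 0.665

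**Power by simulation** (Spearman, t-approximation p-values, first Holm step; independent runs agree to about one point):

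| True rho | Single test at 0.05 | m = 6 | m = 12 | m = 18 | m = 36 |
|---|---|---|---|---|---|
| 0.5 | 57% | 30% | 22% | 19% | 13% |
| 0.6 | 77% | 51% | 41% | 36% | 29% |
| 0.7 | 92% | 75% | 67% | 62% | 53% |

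Holm's later steps recover little: 0.1 point or less with one true correlation, and up to about 3 points in the cases run with several.

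**Hand check.** Power ≈ Φ(atanh(rho)/√(1.06/(n − 3)) − z). For rho = 0.5 and n = 20, the first term is 0.549/0.250 = 2.20.
- Single test: Φ(2.20 − 1.96) = Φ(0.24) ≈ 60%.
- m = 12: Φ(2.20 − 2.865) = Φ(−0.665) ≈ 25%.

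This approximation runs a few points above the simulation at n = 20.

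**Where the loss passes one half**
- rho 0.5: half of 57% is 28.5%. Power is 30% at m = 6 and falls below the line at 7 (simulation) or 8 (approximation).
- rho 0.6: half of 77% is 38.5%. Power crosses it at about 15 or 16 tests by simulation; the approximation gives 22.
- rho 0.7: half of 92% is 46%. Power is still 53% at m = 36, so the line is not crossed in this range.

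**After the fix.** With Holm across two tests, the first step is 0.05/2 = 0.025. Simulated power is about 45% at rho 0.5 and 67% at rho 0.6.

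**The case against.** The strongest reply is that this is a case series of up to 20 patients and the plan itself calls the analysis a screen. Holm in a screen is valid and conservative, estimates will be reported whatever the p-values, and the treatment-effectiveness analysis is untouched. That stands, and it limits the weight of the point. It does not explain why the only stated hypothesis gets no priority.

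Three stronger readings are tempting, and the documents do not support them.
- *That Holm cuts the power by more than half as a general fact.* The family size is undefined and no effect size is given. At rho 0.6 with 12 tests the loss is under half (77% to 41%), and at rho 0.7 it stays under half throughout the range.
- *That the cooling test must survive correction alongside age and smoking.* Membership of the cooling test in the Holm family is the natural reading but is not explicit. The plan says only that confounders will be examined, not that they count towards the family.
- *That nostrils or visits will be pooled as independent rows and inflate false positives.* Nothing says so. Only VAS and peak flow are described by nostril, and repeated measures are recognised in the ANOVA. If rows were pooled with an assumed within-patient correlation of 0.5 in both variables, type I error would be about 8% with two rows per patient and 13% with four. The supportable point is that the unit of analysis is not stated.

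It is also fair to say that the hypothesis names airflow as well as cooling, so a test of cooling alone would cover only part of it. Section 4.9 further allows for an optimal range and non-linear relationships, which one monotone correlation would not capture.

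**Conclusion.** The point holds in a limited form. The only stated hypothesis has no prespecified test, and its one route to a result is a screen with an undefined Holm family. Under the assumptions above, the cost is substantial for moderate correlations and modest for strong ones, as the table shows.

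A reader might infer that the study cannot answer its hypothesis, or that a strong association would usually be missed. Neither follows: at rho 0.7, power stays above one half even with 36 tests. Nor is Holm the only constraint. A single test at 0.05 reaches about 80% power only from a rho of roughly 0.6 (77% by simulation, 79% by approximation), and fewer than 20 complete pairs would lower every figure. The change is worth making because it raises power for the stated question and removes choices after the data are seen, at little cost.

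**What to change.** In 4.9, before data are seen:

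1. Name the hypothesis tests and run them first, outside the screen: simulated valve-region mucosal cooling and simulated valve-region airflow, each against one named primary symptom score (for example NOSE). State the time point or use change from baseline, with one value per patient. Test at two-sided 0.05 with Holm across these two only. Alternatively, test cooling alone at 0.05 if the sponsor names it as the single primary test.
2. Keep Holm for all remaining correlations, list the members of that family, and label them exploratory, including any search for non-linear relationships.
3. If any correlation or regression uses both nostrils or both visits, fit a model with a patient random effect. This is conditional, since the plan does not say that rows will be pooled.

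Error control for the confirmatory claim stays at 0.05, because the tests are fixed in advance.

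**Cost.** No new measurement is needed, but this is more than a wording change. Section 4.6 lists a mucosal cooling rate without defining a valve-region value, so the metrics must be specified. Table 1 places NOSE at screening and CT at baseline, while the list of baseline and follow-up procedures in 4.7 includes NOSE, and 4.6 allows an already prescribed clinical scan as the baseline CT. The plan should therefore state which assessments are paired. The sponsor must commit to one symptom score in advance, and 20 patients will still leave limited power below a rho of about 0.6.

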4.0 PROCEDURES

4.1 Research Design

The study will be conducted by the Department of Otolaryngology, The Ohio State University School of Medicine, in conjunction with Aerin Medical. This study is a prospective, case series design, involving a group of patients with chronic nasal obstruction symptoms. The study is a longitudinal design, involving two test sessions: one at baseline (pre-treatment) and one at 90 days post-treatment.

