4.3 Inclusion Criteria

Eligible subjects will meet all the following:

1. Age 18 to 75 years (inclusively)
2. Willing and able to provide informed consent
3. Willing and able to comply with the subject-specific requirements outlined in the study protocol
4. Complaints of nasal obstruction for at least 1 year
5. Failed maximum medical therapy (4-6 weeks of steroids)
6. Nasal Obstruction Symptom Evaluation (NOSE) score of ≥ 60 at Baseline
7. Nasal valve is a primary or significant contributor to the subject's nasal obstruction as determined by the study investigator (based on clinical presentation, physical examination, nasal endoscopy, etc.) and the subject has a positive response to any of the following temporary measures (based on patient history or during office exam):
 - a. Use of external nasal dilator strips (e.g., Breathe Right Strips)
 - b. Q-Tip test (manual intranasal lateralization)
 - c. Use of nasal stents
 - d. Cottle Maneuver (manual lateral retraction of the cheek; see Figure 4)

[figure not shown]

Figure 4. Cottle Maneuver

Figure 4 demonstrates the Cottle Maneuver as the patient or the physician temporarily lifts and laterizes the skin around the nose and cheek, increasing the nasal valve angle, and potentially increasing nasal airflow. A positive response can be an indicator that the patient will respond well to an increase in nasal valve angle.

The Q-Tip test is another evaluation of potential positive response. A Q-tip is placed gently within the nares against the lateral nasal wall at the location of the narrowest nasal valve region and is pushed outward lightly to expand the nasal valve angle. A positive response to this maneuver may also predict the potential benefit of nasal valve correction.

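### The last step of 4.9 classifies symptom categories in at most 20 subjects with LDA or logistic regression; a penalised model of the score itself, with cut-offs applied afterwards, is a cheap improvement

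*Combined protocol and SAP*

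**What the plan says.** The relevant text is the closing paragraph of 4.9 Data Analysis. It first screens predictors by Spearman correlation and multiple regression, with a Holm–Bonferroni correction. For the last step it gives LDA as one example of a method; as the other example, "logistic regression will be applied for classification and discrimination of patient symptom categories (e.g., symptom-free, moderate and severe nasal obstruction"). Only the predictors found significant enter this step.

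Other sections set the conditions for this step:

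- 4.2 Study Size: "Up to Twenty (20) patients meeting the inclusion/exclusion criteria will be recruited".
- 4.1 Research Design: a longitudinal study "involving two test sessions: one at baseline (pre-treatment) and one at 90 days post-treatment".
- 4.6 Measurement / Instrumentation: the VAS is a linear scale, "range 0-10; 0 being completely clear and 10 being completely blocked". NOSE is also a numeric score.
- 4.3 Inclusion Criteria: "Nasal Obstruction Symptom Evaluation (NOSE) score of ≥ 60 at Baseline". A symptom-free class defined on NOSE is therefore empty at baseline and can arise only at day 90.
- 2.0 Overall Objectives: predicting treatment outcome is an aim, in cautious terms: "The ability to envisage variables that will lead to best outcome may have potential to assist patients and clinicians".

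The plan does not say which score forms the categories, where the cut-offs lie, or how many predictors enter. It also gives no penalty, no rule for an empty category or a model that will not fit, and no internal validation.

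**The concern.** The symptom outcomes are graded, yet the last step works on about three ordered classes. LDA treats the classes as unordered labels. Logistic regression in its usual form takes two classes, or several unordered ones. Neither uses the order, and neither distinguishes a subject just inside a class from one at its far end.

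With at most 20 subjects, a class may hold only a few. If some combination of predictors separates a class from the others, maximum-likelihood logistic regression has no finite coefficients. Two features of the plan push towards this. It expects strong predictors, since 4.9 cites 89.3% success in earlier work. It also chooses the predictors from the same data.

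What is at stake is the exploratory prediction aim: whether the reported classification rule can be estimated, and whether its stated accuracy would hold in new patients.

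**Working it through.** **Inputs.** From the documents: n of at most 20; two visits; about three categories; numeric scores; LDA and logistic regression named. There is no figure of the plan's own to reproduce, because the study size has no derivation. Assumed and varied: a normal latent score; one to three predictors; joint latent R² of 0.25, 0.5 or 0.75; category splits of equal thirds, 20/60/20 and 60/30/10; one row per subject.

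**1. Information kept after cutting the score.** For categories with probability p and mean m on a standard normal score, the share kept is at most Σ p·m².

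- Thirds: m = ±1.091 and 0, so (2/3) × 1.091² = 0.79.
- 20/60/20: m = ±1.400 and 0, so 0.4 × 1.400² = 0.78.
- 60/30/10: m = −0.644, 0.703, 1.755, so 0.6 × 0.415 + 0.3 × 0.494 + 0.1 × 3.080 = 0.70.

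So 21–30% of the information is lost. Matching 20 subjects with the full score would take 20/0.79 to 20/0.70, that is, 26 to 29 subjects.

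**2. No finite logistic fit.** Simulated samples of 20 were tested for separation by an exact linear-programming check on the three-category logit, 400 runs per cell. Results are the percentage of samples with no finite estimate, among those in which all three categories occur:

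| Latent R² | Split | 1 predictor | 2 predictors | 3 predictors |
|---|---|---|---|---|
| 0.25 | thirds | 0.5 | 5 | 13 |
| 0.25 | 20/60/20 | 4 | 13 | 30 |
| 0.25 | 60/30/10 | 9 | 22 | 43 |
| 0.5 | thirds | 6 | 11 | 28 |
| 0.5 | 20/60/20 | 15 | 37 | 50 |
| 0.5 | 60/30/10 | 24 | 42 | 59 |
| 0.75 | thirds | 23 | 41 | 60 |
| 0.75 | 20/60/20 | 40 | 62 | 81 |
| 0.75 | 60/30/10 | 41 | 70 | 84 |

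Sampling error is about 2 points: √(0.28 × 0.72/400) = 0.022. With the 60/30/10 split, roughly a further 11% of samples have an empty category. A separate simulation gave 26–55% for three predictors at R² 0.5. When predictors first had to pass a Holm screen, the range was 3–70%, depending on how correlated the predictors were.

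**3. LDA.** In 1,000 runs per setting with 1 to 10 predictors at n = 20, LDA was finite every time. Its in-sample accuracy was too high. With five pure-noise predictors it appeared to classify 65% correctly against a true 33%. With three predictors and R² 0.5 it appeared to classify 70% against a true 51%.

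**4. The alternative.** A ridge regression of the score, with cut-offs applied to the prediction, was compared with LDA out of sample in 27 simulated settings. It matched or beat LDA in all of them, by 0 to 7 points of accuracy, with lower ordinal error.

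**5. What the alternative costs.** Predicted scores spread less than observed ones: their SD is √R² times the outcome SD. With 20/60/20 cut-offs at ±0.842, the share predicted into each outer class is P(Z > 0.842/√R²). At R² 0.5 this is P(Z > 1.19) = 12%, and at R² 0.25 it is P(Z > 1.68) = 5%, against a true 20%. Ridge shrinkage lowers it further.

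**The case against.** Several arguments on the other side have force.

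*The power loss is misplaced.* A reader might infer that categorising costs the study power to detect predictors. For one predictor with correlation 0.6, power is 84% on the continuous score against 55–60% across three unordered classes. But 4.9 gives detection to the Spearman and regression screen, which is not described as using categories. That reading fails; the loss of information bears only on the classification.

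*LDA does not break down.* A reader might infer that both named methods can fail to produce estimates. Only logistic regression can. LDA's weakness is optimism.

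*The separation rate rests on unstated inputs.* This stands. With one or two predictors, R² up to 0.5 and equal thirds, it is 0.5–11%, and Holm screening at n = 20 may leave few predictors. If both visits were pooled as 40 rows in equal thirds, it was at most 3% for R² up to 0.5, though that ignores within-subject correlation. Saying that the model often fails would go beyond the documents.

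*The text is open-ended.* Methods and categories are given as examples, so a penalised or ordinal model is not excluded. True, but neither is one planned, and the choice could be made after the data are seen.

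*Classification does not need odds ratios.* A separated model still assigns classes in the sample. It then gives fitted probabilities of 0 or 1 for some subjects and no usable coefficients, which is little help in saying which variables matter.

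*The alternative has its own limits.* Compressed predictions are a real drawback. A purely linear model would also miss the optimal range of valve width and shape that 4.9 expects. Both must be dealt with in the fix.

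**Conclusion.** The concern holds in a limited form. The last step of 4.9 discards the order of the categories and about 21–30% of the information in the score, in a study of at most 20 subjects. If unpenalised three-class logistic regression is used at latent R² 0.5, it has no finite estimates in about 11–42% of samples with two predictors and 28–59% with three. Weak predictors and equal categories lower this; strong predictors, unequal categories, or correlated predictors passing the screen together raise it. LDA always fits, but without validation its accuracy would be overstated.

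These sizes rest on assumed normality, predictor number and strength, category splits and one row per subject. None of these is in the documents, so they are ranges and not forecasts.

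A reader might go further and doubt the effectiveness result. The documents do not support that: effectiveness is judged by repeated-measures ANOVA, and this step does not touch it. Only the exploratory prediction aim is affected, so this is a cheap improvement and not a serious defect.

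**What to change.** Reword the last step of 4.9 as follows.

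1. Fit a ridge-penalised regression of the continuous day-90 NOSE, and likewise VAS, on a short predictor set fixed in advance. Add a quadratic term where an optimal range is expected.
2. Fix the category cut-offs in advance and obtain categories by applying them to the predicted score. Agreement with the observed categories can still be reported.
3. If a category model is kept, use an ordinal logistic model with a Firth or ridge penalty in place of plain logistic regression, and state what is done if a category is empty.
4. Report leave-one-out cross-validated accuracy instead of in-sample accuracy. Choose the penalty, and repeat any remaining screening, within each fold.

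The cost is wording only: no extra subjects, visits or measurements. Two downsides should be stated in the plan: coefficients are shrunk and need a sentence of explanation, and predicted scores assign too few subjects to the extreme categories. The quadratic term also spends one more coefficient, which is a reason to keep the predictor set short.
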